- **b. Secondary Specific Aim 2:** ANCOVA models will be used to compare IU-TBANS, PHQ-9, and GAD-7 collected at three months post hospital discharge with group as the independent variable while adjusting for potential baseline covariates.
- **c. Missing Data:** We expect up to 20% of patients who may not complete the primary outcome at day 7 due to death in the ICU or discharge before day 7. We will conduct sensitivity analyses with varying assumptions for the patients with missing outcomes to determine the robustness of our findings. The mixed effects model we propose for Secondary Aim 1 is robust to the missing at random assumption and is unbiased if we include all relevant covariates in the model. We will also compare baseline characteristics of patients with 3-month

assessment and those who are lost to follow-up and adjust for the variables associated with missing data to ensure unbiased estimation and inference.

d. Sex as a Biological Variable: Both male and female patients will be included in the trial. We do not anticipate treatment efficacy will differ by sex. We will include sex as a covariate in each analysis to

determine whether estimated treatment effects differ by sex.

e.Sample Size and Power: Sample size estimation is based on the observed effect size from our pilot data where the intervention group had higher delirium/coma free days from the control group with estimated effect size of 0.52. Using two sample t-test, we estimate that we will need 128 total patients with complete data to detect an effect size of 0.5SD or higher at α =0.05. For robustness of results, we also estimated power if we assume Poisson distribution for mean delirium/coma free days with a total 128 patients observed at day 7, we will have 98.7% power to detect group difference at α =0.05 using the nonparametric Wilcoxon test. Allowing up to 20% attrition rate for patients dropping out before day 7, we will enroll 160 total patients for this trial (80 per group).

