For Aim 2, for anxiety measured by VAS-A, we estimated power using results published by Chlan et al³¹ where the author reported (1) changes in VAS-A in both the music and control groups appear linear; and (2) the music group showed an average difference of 11 points (SD=6.48) in VAS-A scores between the two groups and the noise canceling headphones group had no-significant change over time. Assuming 128 total patients complete anxiety evaluation by day 7, a daily decrease of 0.03SD on VAS-A in the music group and no decrease in the control group, we will have 83.5% power in detecting a group and time interaction in the repeated measure model at α =0.05 assuming a first order autoregressive correlation structure with 0.4 for measurements one day apart. For pain, assuming a baseline mean of 0.54 for both groups (SD=0.63), a daily decrease of 0.2SD on CPOT in the music group and no decrease in the attention control group, we will have 80.6% power to detect a group and time interaction in a mixed effect model. We will also have 80.6% power to detect a significant interaction assuming similar trajectories for CAM-ICU-7 in the two groups. For Aim 3, we will have 80% power to detect an effect size of 0.5SD between the two groups using two sample *t*-test at α =0.05. The power estimates were conducted using the Power and GLMPower procedures in SAS 9.4.

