Exploratory Aim 2: Determine whether the DDM treatment is associated with slower progression of ADRD pathology in older adult ICU survivors as compared to attention control. Hypothesis 2a: Patients in the DDM treatment group will have slower progression in measures of neurodegeneration (lower level of neurofilament light (NfL), phosphorylated tau-181 (p-tau 181), glial fibrillary acidic protein (GFAP), and S100B), AD pathology (higher levels of Aβ42/Aβ40), vascular pathology (lower levels of C-reactive protein (CRP))⁸ and inflammation (lower levels of interleukins (IL)-1, 6, and 8) as measured by blood-based biomarkers collected in the ICU and 3, 6 and 12 months after hospital discharge, compared to those in the attention control group. Hypothesis 2b: These differences in progression of ADRD pathology between the DDM treatment versus control group will be due, in part, to the DDM treatment decreasing the duration and severity of ICU delirium during the index ICU stay.

4. Exploratory Aims Statistical Considerations added (1,2)

Exploratory Aim 1: Mixed effects models will be used with repeated IUTBANS scores (collected at baseline, 6 months and 12 months as the outcome measures), group, time, and a group and time interaction as independent variables while adjusting for stratification variables and other potential baseline covariates found to be significantly different in univariate comparisons. A significant interaction between group and time would indicate differences in changes of cognitive functions over time between the two groups.

Exploratory Aim 2: Changes in the biomarkers will be calculated and used as the dependent variables in ANCOVA models with group as the independent variable and adjusting for stratification variables and baseline covariates that are found to be different among the groups in univariate comparisons. Mixed effects models will be used to explore the association between oxidative stress biomarkers at ICU admission and those collected at 3, 6-, and 12- months post discharge.

5. Revised Figure 3: DDM Trial Flow Chart

6. Revised Table Time-line of Data Collection and Outcomes Assessments

			ata Collection a					
Co	Method of Collection	ne-line of Data Collection and Outcome ICU Phase			Hospital Discharge	Post Hospital Discharge		
		Enrollment	Intervention Phase	Post- intervention phase		3 months	6 months	12 months
Demographics (Age, race, gender, education, Insurance)	EMR	Х						
Clinical Data (lab	EMR	Х						

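### Exploratory Aim 2 fixes neither the scale of the biomarker changes nor the marker's own baseline as a covariate; a simple subtracted change would lose power if the markers are strongly right-skewed

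*Combined protocol and SAP*

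**What the plan says.** The text is in the additional protocol materials of the combined protocol and SAP (amendment of 5/22/2023).

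- **Analysis** (item 4, Exploratory Aim 2): "Changes in the biomarkers will be calculated and used as the dependent variables in ANCOVA models with group as the independent variable".
- **Covariates** (same sentence): "adjusting for stratification variables and baseline covariates that are found to be different among the groups in univariate comparisons". The only stratification variable is hospital location (section 5). The baseline value of the marker under analysis is not named.
- **Markers** (item 3, Hypothesis 2a): nine in all. Eight are concentrations: NfL, p-tau 181, GFAP, S100B, CRP and the interleukins ("inflammation (lower levels of interleukins (IL)-1, 6, and 8"). One is a ratio: "AD pathology (higher levels of Aβ42/Aβ40".
- **Timing**: samples are "collected in the ICU and 3, 6 and 12 months after hospital discharge". The first is drawn before the first session. The analysis paragraph does not say which pair of samples defines the change.

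Nothing is said about a log or percent scale, a check of distribution, a robust or rank-based alternative, or values below an assay limit. The paragraph's other model, a mixed model for oxidative stress markers, explores an association over time and does not compare the arms. The only nonparametric method in the documents, a Wilcoxon test, belongs to the power statement for delirium/coma free days.

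**The concern.** Positive concentrations measured during critical illness can be expected to vary multiplicatively and to have long right tails. If they do, the variance of a subtracted change is set by the few highest values. The change also depends heavily on how high a patient started, above all if levels fall between the ICU and follow-up. ANCOVA on that variable would then often miss a real proportional effect, and the estimated mean difference would mainly describe the extreme patients.

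Leaving the scale open has a second cost: it could be chosen after the data are seen. At stake is the usefulness of an aim for which patients give blood at up to six time points.

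**Working it through.** **1. The plan's own figure.** The plan says "we will need 128 total patients with complete data to detect an effect size of 0.5SD or higher". A two-sided two-sample t-test at 0.05 with a 0.5 SD difference and 64 per arm (128 in total) has 80.1% power, and 128 / (1 − 0.20) = 160 enrolled. The figure reproduces, but it is for the day-7 primary outcome. Exploratory Aim 2 has no stated power, SD or effect.

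**2. Assumed inputs (none is in the documents).** Lognormal marker with the same log-SD *s* at both times; baseline/follow-up correlation ρ = 0.5; multiplicative effect of 0.5*s* on the log scale; no overall shift in level; 64 per arm, borrowed from step 1; two-sided α = 0.05. The effect is a reduction of 1 − e^(−0.5*s*): 14%, 22%, 39% and 53% at *s* = 0.3, 0.5, 1.0 and 1.5.

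**3. Log scale, by formula.**
- Log change has SD *s*√(2(1 − ρ)) = *s*. The standardised effect is 0.5, so power is 80% at every *s*.
- With log baseline as covariate, the residual SD is *s*√(1 − ρ²) = 0.866*s*. The standardised effect is 0.5 / 0.866 = 0.577, so power is 90%.

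**4. Raw change, by formula, at *s* = 1.** Let V = e^(s²)(e^(s²) − 1) = 4.671, C = e^(s²)(e^(ρs²) − 1) = 1.763 and k = e^(−0.5s) = 0.607.
- Mean difference: e^(s²/2)(1 − k) = 0.649.
- Variance of change: control 2V − 2C = 5.815; treated V + k²V − 2kC = 4.250.
- Standard error: √((5.815 + 4.250) / 64) = 0.397.
- Power ≈ Φ(0.649 / 0.397 − 1.96) = Φ(−0.32) = 37%. The normal approximation is rough for data this skewed; simulation gives 42%.

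**5. Simulated power, raw vs log.**

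| log-SD | Change, no baseline covariate | With baseline marker as covariate |
|---|---|---|
| 0.3 | 74% vs 80% | 87% vs 89% |
| 0.5 | 66% vs 81% | 84–86% vs 90% |
| 1.0 | 42% vs 80% | 69% vs 89% |
| 1.5 | 24% vs 80% | 47% vs 89% |

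Entries carry simulation error of about a percentage point; the 84–86% cell shows the spread between runs. With 40 per arm the ratio of log to raw power is similar: 1.1 to 3.6 without the baseline marker and 1.04 to 2.2 with it.

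**6. Influence of extremes.** The 6 most extreme of 128 patients carry 32%, 40%, 63% and 80% of the sum of squares of raw change at log-SD 0.3, 0.5, 1.0 and 1.5. On the log scale they carry 26% throughout.

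**7. If levels fall by one log unit after the ICU.** Raw change without the baseline marker has 15%, 12% and 8% power at log-SD 0.5, 1.0 and 1.5, against 79% for log change. Adding the baseline marker restores raw power to 84%, 68% and 48%.

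**8. Type I error of the raw analysis.** 4.8%, 4.4% and 3.7% at log-SD 0.5, 1.0 and 1.5: no inflation.

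**9. Where the log scale does not help.** For a roughly normal marker with an additive effect and a coefficient of variation of 0.1 to 0.4, log power divided by raw power runs from 1.01 down to 0.92.

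**The case against.** **The plan does not say raw.** A reader might infer that the sponsor has committed to arithmetic differences. The text is silent; log or percent change would also fit it. This stands, so the finding is an unstated scale with a natural default reading, not a wrong scale.

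**A general doubling of power is not shown.** A reader might take the 42% vs 80% row as typical. It needs a log-SD near 1.0 without the baseline marker; with it, a doubling needs about 1.5. At log-SD 0.5, adding the baseline marker to the raw analysis gives at least 84%, more than unadjusted log change. So part of the remedy is the covariate. This stands.

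**The assumed effect grows with the skew.** Fixing it at 0.5 log-SD holds log-scale power near 80% by construction. With a fixed 20% reduction instead (also an assumption), raw vs log power without the baseline marker is 58% vs 71%, 13% vs 23% and 7% vs 13% at log-SD 0.5, 1.0 and 1.5. The log scale is still better, but both analyses would usually miss that effect in a strongly skewed marker. This stands as a caution against reading 80% as what the trial would attain.

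**One or two patients deciding the direction of the estimate** is also tempting to infer. In the scenarios of the table, dropping the two most extreme patients reversed the sign in only about 1%, 5% and 14% of simulated trials at log-SD 0.5, 1.0 and 1.5.

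**The sample size is borrowed.** The number giving blood at months 3 to 12 is not stated. The 40-per-arm results show that the pattern does not depend on it, though the absolute power does.

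None of this supplies the missing specification.

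**Conclusion.** The concern holds as a gap in specification. The documents fix neither the analysis scale nor adjustment for the marker's own baseline, and nothing elsewhere in them fills the gap. If the default reading is followed, the loss runs from negligible (log-SD 0.3) to severe (log-SD 1.5), and it persists in part after baseline adjustment. All sizes rest on assumed lognormal markers, correlation 0.5, a multiplicative effect and 64 per arm.

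The harm is lost power and an unstable estimate. It is not false positives. The aim is exploratory, so the primary and secondary conclusions are untouched. The documents do not support the same statement for the Aβ42/Aβ40 ratio, for which strong skew is not established.

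**What to change.** In item 4 of the additional materials, Exploratory Aim 2:

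1. For the eight concentration markers, make the dependent variable the log follow-up value. Include the log baseline value of the same marker and hospital as covariates. State which sample is the baseline.
2. Report arm differences as ratios of geometric means with 95% intervals.
3. Handle values below the assay limit as censored.
4. For Aβ42/Aβ40, treat the log scale as optional, state the choice in advance, and still adjust for the baseline value.
5. Add a rank-based sensitivity analysis.

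**Cost.** This is a change of wording that needs no new patients or samples, but it is not free. Results become ratios instead of absolute changes, censored values need a suitable model, and power could fall slightly (to about 0.92 of the raw analysis at worst in the cases examined) for a near-symmetric marker with an additive effect.

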Previous research has demonstrated that these tests can be delivered reliably and precisely **in** person or by telephone.⁸⁴

- B. Depression and Anxiety: Research staff will collect PHQ-9 and GAD-7 over the phone or in person prior to/around hospital discharge, at 3 months post-hospital discharge, 6 months post-hospital discharge and 12 months post-hospital discharge.
- 2. Add Blood Sample Collection Time points (month 3, month 6, month 12).

During hospitalization we will collect blood samples prior to first intervention session (up to 10ml in tubes containing anticoagulant), at day 3, and at the end of the intervention period (up to 10 ml in tubes containing anticoagulant). Samples will also be collected at the month 3, month 6 and month 12 post hospital discharge visits (up to 10ml in tubes containing anticoagulant) in the clinic. This will be a total of up to 4 tablespoons of blood collected. The samples will be transported to the CTSI lab, and will be prepared and stored using deidentified labels.

3. Exploratory Aims added (1,2):

Exploratory Aim 1: Test the efficacy of the DDM treatment in slowing the rate of post-ICU cognitive decline in mechanically ventilated patients as compared to attention control. Hypothesis 1a: Patients in the DDM intervention group will have slower cognitive decline compared to the attention control group as measured by the IU-TBANS completed at 6- and 12-months after hospital discharge. Hypothesis 1b: This difference in cognitive trajectories between the DDM intervention group versus the attention control group will be due, in part, to the DDM treatment decreasing the duration and severity of ICU delirium during the index ICU stay.

[figure not shown]

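### Exploratory Aim 2 compares nine biomarkers by ANCOVA on an unnamed change; one baseline-adjusted repeated-measures model per marker would use all the samples and fix what is tested

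*Combined protocol and SAP*

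**What the plan says.** All the relevant text is in the Additional Protocol Materials based on Supplemental Funding (amendment of 5/22/2023).

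- **Hypothesis (item 3, Exploratory Aim 2).** Hypothesis 2a predicts slower progression in the music arm, "as measured by blood-based biomarkers collected in the ICU and 3, 6 and 12 months after hospital discharge". The markers are "neurofilament light (NfL), phosphorylated tau-181 (p-tau 181), glial fibrillary acidic protein (GFAP), and S100B), AD pathology (higher levels of Aβ42/Aβ40" (five measures), "vascular pathology (lower levels of C-reactive protein (CRP" (one) and "inflammation (lower levels of interleukins (IL)-1, 6, and 8" (three), nine in all.
- **Sampling (item 2).** Blood is drawn before the first session, at day 3 and at the end of the intervention. After that: "Samples will also be collected at the month 3, month 6 and month 12 post hospital discharge visits", in the clinic. That makes up to six samples per patient.
- **Group comparison (item 4, Exploratory Aim 2).** "Changes in the biomarkers will be calculated and used as the dependent variables in ANCOVA models with group as the independent variable", with covariates described as "adjusting for stratification variables and baseline covariates that are found to be different among the groups in univariate comparisons". No visit, time term, group-by-time term or deciding contrast is given, and there is no significance level or multiplicity rule for this aim. A mixed model does appear under this aim, but it relates oxidative stress markers at ICU admission to later values and does not estimate the group effect.
- **Neighbouring aim (item 4, Exploratory Aim 1).** "Mixed effects models will be used with repeated IUTBANS scores", with group, time and their interaction.
- **Missing data (Statistical Considerations, item c).** The text covers the day 7 outcome, Secondary Aim 1 and the 3-month assessment. It does not mention biomarkers.

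**The concern.** The hypothesis is about a course over time, but the stated analysis takes one change as its outcome. Three consequences follow if that change runs from baseline to a single visit.

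1. Each estimate uses one follow-up visit, and nothing says how months 3, 6 and 12 are brought together.
2. A patient without a sample at a visit contributes nothing to that visit's estimate, even when the other samples exist. Follow-up blood needs a clinic visit, whereas mood may be assessed by phone or in person, so some missed draws are plausible.
3. A change score without the baseline value as a covariate is less precise than an analysis that adjusts for it. The plan adds baseline covariates only where the arms differ.

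At stake is how firmly a statement that music slows ADRD pathology could be read. Under the present text, any marker at any visit could be offered in support.

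**Working it through.** The plan states no sample size, power or error rate for this aim, so there is no figure to reproduce. The main sample size does reproduce: a two-sample t-test at 0.5 SD, 80% power and α = 0.05 needs 64 per arm, so 128, and 128/0.8 = 160. It does not bear on the biomarkers.

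**Inputs from the documents:** nine markers, three post-discharge visits, one pre-intervention sample, 160 patients enrolled.

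**Assumptions (the documents give no values):** marker variance 1 at each draw; the same correlation r, 0.3 to 0.8, between any two draws; a fraction m, 0 to 40%, missing independently at each follow-up visit; deaths ignored; 0.05 two-sided per test.

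**Who contributes.** Take m = 20%. A single-visit analysis uses 160 × 0.8 = 128 patients. A repeated-measures model uses everyone with at least one follow-up draw: 160 × (1 − 0.2³) ≈ 159. All three draws are available for 160 × 0.8³ ≈ 82.

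**Variance per enrolled patient (common factors cancel)**

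- Single-visit change score: 2(1 − r)/(1 − m).
- Baseline-adjusted mean of three visits, complete data: (1 + 2r)/3 − r².
- The same with missing draws: given baseline, the visits have variance 1 − r² and covariance r − r². For each pattern of observed visits, invert that part of the matrix, weight by the pattern's probability, sum, invert the sum, and take the variance of the average.

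| m | r | Change score, one visit | Adjusted mean of three | Ratio |
|---|---|---|---|---|
| 0 | 0.3 | 1.40 | 0.443 | 3.2 |
| 0 | 0.5 | 1.00 | 0.417 | 2.4 |
| 0 | 0.8 | 0.40 | 0.227 | 1.8 |
| 0.2 | 0.3 | 1.75 | 0.514 | 3.4 |
| 0.2 | 0.5 | 1.25 | 0.471 | 2.7 |
| 0.2 | 0.8 | 0.50 | 0.250 | 2.0 |
| 0.4 | 0.3 | 2.33 | 0.635 | 3.7 |
| 0.4 | 0.5 | 1.67 | 0.566 | 2.9 |
| 0.4 | 0.8 | 0.67 | 0.293 | 2.3 |

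**Where the gain comes from (complete data).** A single visit adjusted for baseline has variance 1 − r².

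- At r = 0.3: baseline adjustment gives 1.40/0.91 = 1.54 and averaging gives 0.91/0.443 = 2.05. The product is 3.2.
- At r = 0.8: 0.40/0.36 = 1.11 and 0.36/0.227 = 1.59. The product is 1.8.

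If month 12 is the deciding contrast instead, the same model has 1.1 to 1.6 times the information of the month 12 change score over the same ranges.

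**The baseline term is essential.** Without it, the three-visit mean has variance (1 + 2r)/3. At r = 0.8 that is 0.867, worse than the 0.40 of a single-visit change score.

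**False positives with no true effect**

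- Nine independent tests: 1 − 0.95⁹ = 37%.
- Nine markers at three visits, 27 independent tests: 1 − 0.95²⁷ = 75%.
- The 27 tests by simulation: 51 to 72% with correlation 0 to 0.4 between markers and 0.4 to 0.8 between visits; 46% at 0.5 and 0.8.
- Counting only results that favour music among the 27: 1 − 0.975²⁷ = 49.5% if independent, and 26 to 46% under the first set of correlations.

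**The case against.** The strongest reply is that the text is underspecified rather than wrong. A change can be a mean change over visits or a slope per patient, and ANCOVA accepts either. This stands in part. With complete data, mean change over three visits has variance (1 + 2r)/3 + 1 − 2r, which is 0.933, 0.667 and 0.267 at r = 0.3, 0.5 and 0.8. The proposed model's advantage over it is then 2.1, 1.6 and 1.2, from baseline adjustment alone. But the plan does not say that visits are averaged, and a patient with a missed draw would still need a rule.

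A second reply is that the aim is labelled exploratory, was added with supplemental funding, and supports no primary or secondary result. This is a good reason not to demand strict error control. It does not explain why the tested change is left open when the neighbouring aim has a repeated-measures model.

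A reader might go further in two ways that the documents do not support:

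- **That a false positive on some marker is more likely than not.** This needs 27 separate tests, and the plan does not specify one per marker and visit. With one test per marker the figure is 37%. Even with 27, it can fall below one half under stronger correlation, or when only results favouring music are counted.
- **That patients who miss a clinic draw are lost.** With visit-by-visit change scores they leave only the visit they miss. Complete loss would need a single analysed visit or a complete-case rule, and the text states neither. Nor do the documents give attrition for months 3 to 12, so nothing shows that biomarkers will have the most missing data of any outcome.

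**Conclusion.** The concern holds as a weakness in the stated method that wording can cure. The group comparison does not match a hypothesis about progression, leaves the tested change open, says nothing on missed draws, and does not routinely adjust for the marker's own baseline.

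The size depends on assumptions: a factor of 1.8 to 3.7 in information for the averaged contrast against one single-visit change score, with equal correlations of 0.3 to 0.8 and 0 to 40% missing independently per visit. Part of that factor is the choice to average visits, which is a different quantity from the effect at one visit. The false-positive range of 37% to 75% describes how the results should be read; it is not evidence of a design error, and the change of model alone would still leave about 37% over nine independent tests.

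**What to change.** In item 4, Exploratory Aim 2, replace the change-score ANCOVA with one mixed model for repeated measures per marker:

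- **Outcomes:** all post-baseline samples.
- **Terms:** group, visit, group-by-visit, hospital stratum, the marker's value before the first session, and that value's interaction with visit.
- **Deciding contrast:** one per marker, named before biomarker results are seen by arm. Examples are the baseline-adjusted group difference averaged over months 3, 6 and 12, or the difference at month 12 if the effect is expected to grow. Visit-specific estimates are descriptive.
- **Interpretation:** state that the results are hypothesis-generating. False-discovery-rate control over the nine deciding tests is optional; it would make each marker's threshold somewhat stricter.

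The cost is wording only, with no new patients, visits or assays. Single-visit findings lose standing as separate claims, and the model relies on missed draws being missing at random given the data in the model, an assumption that the plan should state.
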